## 6.2.12. Visits 14 and 16 (Clinic Visits)

The procedures outlined in [Table 6-12](#) will be performed at Visits 14 and 16.

**Table 6-12. Procedures and Assessments at Visits 14 and 16**

Assessment or Procedure	Explanation
FACT-Leu	HRQL instrument ( Appendix 2 ) to be administered before any other procedures are performed and before any study-related information is communicated to the subject
EQ-5D	Health utility instrument ( Appendix 4 ) to be administered after FACT-Leu but before other procedures are performed and before study-related information is communicated to the subject
Adverse events	Recording of adverse events occurring since the last clinic visit
Assessment of Diarrhea / Colitis	Obtain history of onset and duration of diarrhea, including description of number of stools and stool composition (eg, watery, bloody, nocturnal), travel history, dietary changes and a medication review to identify possible diarrheogenic agents Perform physical examination including assessment for fever, dizziness, abdominal pain/cramping, and weakness (ie, evaluate for sepsis, bowel obstruction, dehydration)
Concomitant medications	Recording of concomitant medication use since the last clinic visit
Performance status	Using Karnofsky performance status criteria ( Appendix 3 )
Oxygen saturation	To be assessed by pulse oximetry while subject is breathing room air
Physical examination	Including assessment of weight, lymph nodes, spleen, and liver
Urine $\beta$ -HCG dipstick	For women of child-bearing potential only
Hematology	Including hematocrit, hemoglobin, erythrocyte count; absolute counts of leukocytes, neutrophils, lymphocytes, monocytes, eosinophils, basophils, platelet count
Serum chemistry	Including sodium, potassium, chloride, glucose, urea, creatinine, calcium, phosphorus, total protein, albumin, ALT, AST, ALP, GGT, total bilirubin, LDH, uric acid, cholesterol, triglycerides
Circulating cells	Including cells for analysis of PI3K/AKT/mTOR pathway activation and quantitation of CD4+, CD5+, CD8+, CD16/CD56+, CD19+, and CD+20 cells by flow cytometry
Biomarkers	Collection of plasma and serum for evaluation of circulating chemokines and cytokines
CMV Surveillance	Arm A only: Surveillance for active disease must be conducted approximately every 4 weeks.
Serum Igs	Including quantitative levels of IgA, IgE, IgG, and IgM
IWRS access	Access of IWRS to document subject visit and to obtain kit numbers (if applicable)

**Abbreviations:**  $\beta$ -HCG= beta human chorionic gonadotropin, AKT=AKT (a serine/threonine protein kinase), ALP=alkaline phosphatase, ALT=alanine aminotransferase, AST=aspartate aminotransferase, EQ-5D=EuroQoL Five-Dimension, FACT-Leu=Functional Assessment of Cancer Therapy-Leukemia, HRQL=health-related quality of life, GGT=gamma-glutamyltransferase, Ig=immunoglobulin, IWRS=interactive web response system, LDH=lactate dehydrogenase, mTOR=mammalian target of rapamycin, PI3K=phosphatidylinositol 3-kinase, CMV Surveillance= Arm A only: Surveillance for active disease must be conducted approximately every 4 weeks.

### 6.2.13. Visits 15 and 17 (Clinic and Radiology Visits)

The procedures outlined in [Table 6-13](#) will be performed at Visits 15 and 17.

**Table 6-13. Procedures and Assessments at Visits 15 and 17**

Assessment or Procedure	Explanation
Pre-Visit Tumor Assessment	
Radiology assessment	CT or MRI imaging of neck, chest, abdomen, and pelvis within 1 week of the visit; the same method of assessment (CT or MRI) should be used as was used at baseline.
Visit Procedures and Assessments	
FACT-Leu	HRQL instrument ( Appendix 2 ) to be administered before any other procedures are performed and before any study-related information is communicated to the subject
EQ-5D	Health utility instrument ( Appendix 4 ) to be administered after FACT-Leu but before other procedures are performed and before study-related information is communicated to the subject
Adverse events	Recording of adverse events occurring since the last clinic visit
Assessment of Diarrhea / Colitis	Obtain history of onset and duration of diarrhea, including description of number of stools and stool composition (eg, watery, bloody, nocturnal), travel history, dietary changes and a medication review to identify possible diarrheogenic agents Perform physical examination including assessment for fever, dizziness, abdominal pain/cramping, and weakness (ie, evaluate for sepsis, bowel obstruction, dehydration)
Concomitant medications	Recording of concomitant medication use since the last clinic visit
Study drug return/accounting	Counting returned idelalisib
Performance status	Using Karnofsky performance status criteria ( Appendix 3 )
Oxygen saturation	To be assessed by pulse oximetry while subject is breathing room air
Physical examination	Including assessment of weight, lymph nodes, spleen, and liver
Urine $\beta$ -HCG dipstick	For women of child-bearing potential only; also performed 6 weeks ( $\pm$ 5 days) following Visit 17
Hematology	Including hematocrit, hemoglobin, erythrocyte count; absolute counts of leukocytes, neutrophils, lymphocytes, monocytes, eosinophils, basophils, platelet count
Serum chemistry	Including sodium, potassium, chloride, glucose, urea, creatinine, calcium, phosphorus, total protein, albumin, ALT, AST, ALP, GGT, total bilirubin, LDH, uric acid, cholesterol, triglycerides
HBV DNA by PCR	Only subjects who are HBc antibody positive and HBV DNA negative at screening, per Section 5.4.5 .
Circulating cells	Including cells for analysis of PI3K/AKT/mTOR pathway activation and quantitation of CD4+, CD5+, CD8+, CD16/CD56+, CD19+, and CD+20 cells by flow cytometry
Biomarkers	Collection of plasma and serum for evaluation of circulating chemokines and cytokines
Serum Igs	Including quantitative levels of IgA, IgE, IgG, and IgM

Assessment or Procedure	Explanation
CMV Surveillance	Arm A only: Surveillance for active disease must be conducted approximately every 4 weeks.
Bone marrow biopsy and/or aspirate	To be performed post-baseline to confirm CR or PD. If the subject does not otherwise meet criteria for CR or if the nature of PD does not require bone marrow confirmation, it is not necessary to obtain a follow-up bone marrow biopsy/aspirate
IWRS access	Access of IWRS to document subject visit and to obtain kit numbers (if applicable)
Study drug dispensing (Arm A)	Dispensing of 12-week supply of idelalisib to the subject with instructions for self-administration at home

**Abbreviations:**  $\beta$ -HCG= beta human chorionic gonadotropin, AKT=AKT (a serine/threonine protein kinase), ALP=alkaline phosphatase, ALT=alanine aminotransferase, AST=aspartate aminotransferase, CT=computed tomography, EQ-5D=EuroQoL Five-Dimension, FACT-Leu=Functional Assessment of Cancer Therapy-Leukemia, HRQL=health-related quality of life, GGT=gamma-glutamyltransferase, Ig=immunoglobulin, IWRS=interactive web response system, LDH=lactate dehydrogenase, MRI=magnetic resonance imaging, mTOR=mammalian target of rapamycin, PI3K=phosphatidylinositol 3-kinase

#### 6.2.14. Visit 18 and Subsequent Visits (Every 12 Weeks) (Clinic and Radiology Visits)

The procedures outlined in [Table 6-14](#) will be performed at Visit 18 and subsequent visits (every 12 weeks).

**Table 6-14. Procedures and Assessments at Visit 18 and Subsequent Visits (Every 12 Weeks)**

Assessment or Procedure	Explanation
Pre-Visit Tumor Assessment	
Radiology assessment	CT or MRI imaging of neck, chest, abdomen, and pelvis within 1 week of the visit; the same method of assessment (CT or MRI) should be used as was used at baseline.
Visit Procedures and Assessments	
FACT-Leu	HRQL instrument ( Appendix 2 ) to be administered before any other procedures are performed and before any study-related information is communicated to the subject
EQ-5D	Health utility instrument ( Appendix 4 ) to be administered after FACT-Leu but before other procedures are performed and before study-related information is communicated to the subject
Adverse events	Recording of adverse events occurring since the last clinic visit
Assessment of Diarrhea / Colitis	Obtain history of onset and duration of diarrhea, including description of number of stools and stool composition (eg, watery, bloody, nocturnal), travel history, dietary changes and a medication review to identify possible diarrheogenic agents Perform physical examination including assessment for fever, dizziness, abdominal pain/cramping, and weakness (ie, evaluate for sepsis, bowel obstruction, dehydration)
Concomitant medications	Recording of concomitant medication use since the last clinic visit
Study drug return/accounting	Counting returned idelalisib

Assessment or Procedure	Explanation
Performance status	Using Karnofsky performance status criteria ( Appendix 3 )
Oxygen saturation	To be assessed by pulse oximetry while subject is breathing room air
Physical examination	Including assessment of weight, lymph nodes, spleen, and liver
Urine $\beta$ -HCG dipstick	For women of child-bearing potential only; also performed 6 weeks ( $\pm$ 5 days) following Visit 18 and subsequent visits
Hematology	Including hematocrit, hemoglobin, erythrocyte count; absolute counts of leukocytes, neutrophils, lymphocytes, monocytes, eosinophils, basophils, platelet count
Serum chemistry	Including sodium, potassium, chloride, glucose, urea, creatinine, calcium, phosphorus, total protein, albumin, ALT, AST, ALP, GGT, total bilirubin, LDH, uric acid, cholesterol, triglycerides
HBV DNA by PCR	Only subjects who are HBc antibody positive and HBV DNA negative at screening, per Section 5.4.5 .
Circulating cells	Including cells for analysis of PI3K/AKT/mTOR pathway activation and quantitation of CD4+, CD5+, CD8+, CD16/CD56+, CD19+, and CD+20 cells by flow cytometry
Biomarkers	Collection of plasma and serum for evaluation of circulating chemokines and cytokines
Serum Igs	Including quantitative levels of IgA, IgE, IgG, and IgM
CMV Surveillance	Arm A only: Surveillance for active disease must be conducted approximately every 4 weeks.
PJP prophylaxis	Subjects must receive trimethoprim-sulfamethoxazole or other established prophylaxis for PJP throughout the course of idelalisib treatment and for 2 to 6 months after the last dose of idelalisib and until the CD4+ T-cell count is documented to be >200 cells/mL.
Serum complement	CH50
Bone marrow biopsy and/or aspirate	To be performed post-baseline to confirm CR or PD. If the subject does not otherwise meet criteria for CR or if the nature of PD does not require bone marrow confirmation, it is not necessary to obtain a follow-up bone marrow biopsy/aspirate
IWRS access	Access of IWRS to document subject visit and to obtain kit numbers (if applicable)
Study drug dispensing (Arm A)	Dispensing of 12-week supply of idelalisib to the subject with instructions for self-administration at home

**Abbreviations:**  $\beta$ -HCG= beta human chorionic gonadotropin, AKT=AKT (a serine/threonine protein kinase), ALP=alkaline phosphatase, ALT=alanine aminotransferase, AST=aspartate aminotransferase, CT=computed tomography, EQ-5D=EuroQoL Five-Dimension, FACT-Leu=Functional Assessment of Cancer Therapy-Leukemia, HRQL=health-related quality of life, GGT=gamma-glutamyltransferase, Ig=immunoglobulin, IWRS=interactive web response system, LDH=lactate dehydrogenase, MRI=magnetic resonance imaging, mTOR=mammalian target of rapamycin, PI3K=phosphatidylinositol 3-kinase, CMV Surveillance= Arm A only: Surveillance for active disease must be conducted approximately every 4 weeks.

### 6.2.15. End-of-Study Visit (Clinic Visit)

At the time of discontinuation from the study, the subject should have the procedures and assessments performed as documented in [Table 6-15](#). An end-of-study CT/MRI tumor assessment should be performed unless the subject already has radiographic confirmation of definitive disease progression or a CT/MRI has been performed within 4 weeks prior to the end-of-study visit.

**Table 6-15. Procedures and Assessments at End-of-Study Visit**

Assessment or Procedure	Explanation
Radiology assessment a	CT or MRI imaging of neck, chest, abdomen, and pelvis; the same method of assessment (CT or MRI) should be used as was used at baseline
FACT-Leu	HRQL instrument ( Appendix 2 ) to be administered before any other procedures are performed
EQ-5D	Health utility instrument ( Appendix 4 ) to be administered after FACT-Leu but before any other procedures are performed
Adverse events	Recording of adverse events occurring since prior visit; if a clinically significant adverse event or abnormal result is observed that is not resolved by the end-of-treatment visit, repeat evaluations should be performed to document resolution or stabilization of the abnormality
Assessment of Diarrhea / Colitis	Obtain history of onset and duration of diarrhea, including description of number of stools and stool composition (eg, watery, bloody, nocturnal), travel history, dietary changes and a medication review to identify possible diarrheogenic agents Perform physical examination including assessment for fever, dizziness, abdominal pain/cramping, and weakness (ie, evaluate for sepsis, bowel obstruction, dehydration)
Concomitant medications	Recording of concomitant medication used since prior visit
Study drug return/accounting	Counting returned idelalisib
Performance status	Using Karnofsky performance status criteria ( Appendix 3 )
Oxygen saturation	To be assessed by pulse oximetry while subject is breathing room air
Physical examination	Including assessment of weight, lymph nodes, spleen, and liver
Serum $\beta$ -HCG	Women of child-bearing potential only
CLL peripheral blood evaluation	Including FISH for chromosome 11q deletion, 13q deletion, 17p deletion and 12 trisomy; DNA mutational analysis for TP53, IGHV (including IgHV3-21), and other genes of interest in CLL (eg, Notch); flow cytometry for CD5, CD10, CD11c, CD19, CD20, CD23, CD38, CD45, kappa and lambda light chains, and ZAP-70; cytology for karyotyping; bone marrow aspirate may be used if peripheral blood lymphocyte count is too low
CLL serology	Serum $\beta$ 2 microglobulin
Urine $\beta$ -HCG dipstick	For women of child-bearing potential only

**CCI**

Assessment or Procedure	Explanation
Hematology	Including hematocrit, hemoglobin, erythrocyte count; absolute counts of leukocytes, neutrophils, lymphocytes, monocytes, eosinophils, basophils, platelet count
Serum chemistry	Including sodium, potassium, chloride, glucose, urea, creatinine, calcium, phosphorus, total protein, albumin, ALT, AST, ALP, GGT, total bilirubin, LDH, uric acid, cholesterol, triglycerides
Circulating cells	Including cells for analysis of PI3K/AKT/mTOR pathway activation and quantitation of CD4+, CD5+, CD8+, CD16/CD56+, CD19+, and CD+20 cells by flow cytometry
Biomarkers	Collection of plasma and serum for evaluation of circulating chemokines and cytokines
Serum Igs	Including quantitative levels of IgA, IgE, IgG, and IgM
Serum complement	CH50
PJP prophylaxis	Subjects must receive trimethoprim-sulfamethoxazole or other established prophylaxis for PJP throughout the course of idelalisib treatment and for 2 to 6 months after the last dose of idelalisib and until the CD4+ T-cell count is documented to be >200 cells/mcL.
IWRS	Access IWRS to document that subject has permanently discontinued study therapy

a An end-of-study CT/MRI tumor assessment should be performed unless the subject already has radiographic confirmation of definitive disease progression or a CT/MRI has been performed within 4 weeks prior to end-of-study.

**Abbreviations:** β-HCG=beta human chorionic gonadotropin, AKT=AKT (a serine/threonine protein kinase), ALP=alkaline phosphatase, ALT=alanine aminotransferase, AST=aspartate aminotransferase, CLL=chronic lymphocytic leukemia, CT=computed tomography, EQ-5D=EuroQoL Five-Dimension, FACT-Leu=Functional Assessment of Cancer Therapy-Leukemia, FISH= fluorescence in-situ hybridization, GGT=gamma-glutamyltransferase, Ig=immunoglobulin, IgHv=immunoglobulin heavy-chain variable-region, IWRS=interactive web response system, LDH=lactate dehydrogenase, MRI=magnetic resonance imaging, mTOR=mammalian target of rapamycin, PI3K=phosphatidylinositol 3-kinase, RNA=ribonucleic acid, ZAP-70=zeta-associated protein 70, CMV Surveillance= Arm A only: Surveillance for active disease must be conducted approximately every 4 weeks.

[figure not shown]
### 6.2.16. 30 Day and Long-Term Follow-up

A 30 Day follow-up visit will be performed 30 days (± 5 days) following the end-of-study visit; however, it may be waived for subjects who have permanently discontinued study drug and have had a study visit > 30 days after the last dose of study drug.

Long-term follow-up will be conducted at annual intervals (± 4 weeks) for 5 years, starting at the EOS visit. Information may be gathered during a routine clinic visit or other contact with the subject, or via telephone. Information gathered will include medical status, anti-tumor treatments, secondary malignancies, and survival status.

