### **5.9. Discontinuation from Study**

Subject study participation may be ended due to any of the following reasons:

- Disease progression (confirmed by the IRC)
- Withdrawal of consent
- Initiation of other anticancer therapy
- Physician's decision to remove the subject from the study
- Pregnancy
- The subject is lost to follow-up
- Death
- Discontinuation of study by the Sponsor, a Regulatory Agency, or an IRB or EC

Subjects who permanently discontinue study drug(s) for a reason other than disease progression (as determined by the IRC) shall continue with assessments per the schedule of procedures until disease progression or until study participation is ended.

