- DOR: Data from surviving, non-progressing subjects will be censored at the earliest of the time of initiation of antitumor treatment other than the study treatment or the last time that lack of definitive CLL progression was objectively documented.
- OS: Data from surviving subjects will be censored at the last time that the subject was known to be alive.

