### 9.5. Sample Size

Based on data from the Phase 2 pivotal study ofatumumab {[Wierda 2010](#)} and considering the population of subjects to be enrolled to this study, it is reasonable to assume that administration of ofatumumab to subjects with previously treated CLL in Arm B of this trial will result in a median PFS of ~8 months. An improvement in median PFS from 8 months to 14 months due to the addition of idelalisib to ofatumumab in Arm A of the study would correspond to a benefit ratio of 1.75 (hazard ratio 0.57).

It is assumed that PFS times are exponentially distributed in each of the 2 arms. With a hazard ratio equal to 1 under the null hypothesis of no difference between the 2 treatment arms and a hazard ratio of 0.57 under the alternative hypothesis of superiority of the idelalisib-containing combination, 129 events (definitive CLL progressions or deaths) are required to achieve a power of >0.85 based on a log-rank test with a 2-sided significance level of 0.05. Further assuming a planned accrual period of 12 months (with approximately half of the subjects enrolled during the initial 60% of the accrual period, and the remaining half of the subjects enrolled during the last 40% of the accrual period), a minimum follow-up period of 12 months, and an expectation that 10% of subjects will be lost to follow-up (5% during the accrual period and 5% during the follow-up period), and to ensure the primary analysis on PFS will be performed before or at the planned minimum 12-month follow-up period, 170 subjects will be enrolled into Arm A and 85 subjects will be enrolled into Arm B in order to achieve the expected number of events by the end of the planned minimum 12-month follow-up period. If the planned subject enrollment does not appear adequate to accrue the expected number of events within the proposed follow-up period, the sample size may be adjusted upward.

It is expected that there will be approximately 65 deaths at the time of final analysis. This would provide ~85% power to detect a HR of 0.45 for overall survival based on a log-rank test at 2-sided alpha level of 0.03.

The resulting safety data set provided by the idelalisib-treated subjects (N=170) compares favorably with the safety data set derived from the initial pivotal registration trials for ofatumumab (N=138) {[Wierda 2010](#)}, oral fludarabine (N=78) {[Boogaerts 2001](#)}, or alemtuzumab (N=93) {[Keating 2002a](#)}.

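### Survival contact after end of study is only annual and no survival update is tied to the PFS-driven data cuts, so many post-progression deaths could be unrecorded when OS is tested

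*Protocol*

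**What the plan says.** Section 6.2.16: "Long-term follow-up will be conducted at annual intervals", with a window of 4 weeks either side, for 5 years from the end-of-study visit. The content is set by "Information gathered will include medical status, anti-tumor treatments, secondary malignancies, and survival status", and the mode is open: "Information may be gathered during a routine clinic visit or other contact with the subject, or via telephone". The only contact between the end-of-study visit and the first annual one is the visit introduced by "A 30 Day follow-up visit will be performed 30 days", which may be waived for some subjects. Appendix 7 adds no other.

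Section 5.9 lists IRC-confirmed progression among the events that may end participation. A subject who stops drug without progression stays on the regular visit schedule.

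Section 9.5: "It is expected that there will be approximately 65 deaths at the time of final analysis". This is said to give about 85% power for a hazard ratio of 0.45 at two-sided 0.03. Section 9.4.1.6 makes OS one of five sequentially tested secondary endpoints, and the synopsis lets them be tested at an interim or the final analysis once PFS is rejected. Section 9.3.2.2 sets the censoring: "OS: Data from surviving subjects will be censored at the last time that the subject was known to be alive". Section 9.6.2 triggers the final analysis at about 129 PFS events and names only query resolution before database lock.

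**The concern.** The contact schedule and the OS analysis run on different clocks. OS is read when PFS events reach a count, while survival after progression is asked for once a year. A subject who progressed a few months before the cut has had at most a 30-day visit and is censored close to the end-of-study date, even if since dead.

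Safety reporting does not fill the gap. Under Section 8.3, investigators need not actively seek serious adverse events after the 30-day period. Under Section 8.4.1, death from CLL progression is not a serious adverse event unless study drug is judged to have contributed.

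At stake are the information behind a type-I-error-controlled test and the early check on mortality that Section 3.5.2.1 gives as a reason for measuring OS.

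**Working it through.** **1. The plan's own figures.** With 2:1 allocation, power = Φ(√(d·p(1−p))·|ln HR| − z).
- PFS: d = 129, HR 0.57, p = 2/3, z = 1.960. √(129 × 2/9) × 0.562 = 3.01, so power = Φ(1.05) = 0.853. This reproduces the stated value above 0.85.
- OS: d = 65, HR 0.45, z = 2.170. With p = 2/3, power is 0.806. With the event split expected under the alternative, p = 0.90/1.90 = 0.474, it is Φ(4.026 × 0.799 − 2.170) = 0.852. Simulated log-rank tests with 170:85 subjects give 0.845 to 0.865. The stated 85% or so is therefore sound if 65 deaths are known. The count of 65 cannot be derived, because no OS median is given.

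**2. Who can have had an annual contact.** Section 9.5 gives PFS medians of 14 and 8 months, 12 months' accrual with half enrolled in the first 60% (0.6 × 12 = 7.2 months), 170:85 subjects and 10% loss. Simulated on these inputs, the 129th PFS event falls near month 19.
- Final cut at month 19: an annual contact requires end of study by about month 19 − 12 = 7, when only about half of the subjects have been enrolled.
- First interim, near month 12: it requires end of study by about month 0, or about month 1 using the 4-week window, so almost nobody qualifies.

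Four illustrative scenarios assumed that 10% to 20% of PFS events are deaths, with monthly post-progression death hazards of 0.05 to 0.12 in Arm B and 0.03 to 0.05 in Arm A:

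| Cut | Approx. month | Progressed | Reached an annual contact | Post-progression deaths known |
|---|---|---|---|---|
| 50% interim | 12 | 52–58 | essentially 0 | not tabulated |
| 75% interim | 15 | 78–87 | 4–5 | 5–6 of 17–20 |
| 129 events | 19 | 103–116 | 19–22 | 12–15 of 30–35 |

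Median time since progression at the 129-event cut was 7.3 months.

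**3. Deaths known if about 65 have occurred.** Progression or dropout leads to end of study. Later deaths count as known only if a scheduled contact (30 days, 12 months, 24 months and so on) falls between the death and the cut. Post-progression survival, taken as equal in both arms, was set so that about 65 deaths had occurred by the cut. Power uses the event-split formula of step 1.

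| Cut | Death share of PFS events | Post-progression deaths unknown | All deaths known | OS power |
|---|---|---|---|---|
| Month 19 | 5% | 59% | 30 | 0.50 |
| Month 19 | 20% | 59% | 41 | 0.65 |
| Month 19 | 40% | 60% | 57 | 0.80 |
| Month 24 | 5% | 45% | 39 | 0.63 |
| Month 24 | 20% | 46% | 50 | 0.74 |
| Month 24 | 30% | 46% | 57 | 0.80 |

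In runs that also varied post-progression survival (medians of 6 to 24 months), the unknown share of post-end-of-study deaths was 58% to 61% at month 19 and 42% to 46% at month 24. At month 24 a 40% death share could not be matched to 65 deaths. The power column assumes that the known deaths still show a hazard ratio of 0.45.

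**The case against.** The best defence is that Section 6.2.16 sets a contact schedule and does not prohibit other contact. It allows telephone or any other route, so a survival sweep before lock would comply with the text. The SAP or data-management documents, not available here, may provide for one. Section 9.6.3 also allows later OS follow-up. All of this stands, and it rules out the reading that the 65 deaths could not be counted. It does not remove the point. The interval binding on sites is set in the protocol, and following it as written gives a poorer OS result.

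A reader might also infer that most OS deaths would be missed. The figures do not support that in general. Deaths before progression are captured at regular visits, and in all but the most adverse month-19 case above (30 of about 64 known) at least half of all deaths are known. The statement that most are unknown applies to post-progression deaths at a cut near month 19. Section 9.6.2 expects at least about 12 months of follow-up, which with 12 months' accrual means month 24, and there the share is under half. Section 9.5, however, plans the analysis before or at that point, so month 24 is the late end.

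A third inference is strong bias between arms. In one scenario (20% death share, monthly hazards 0.09 in Arm B and 0.03 in Arm A), the share of post-progression deaths known was similar, about 42% in Arm B and 40% in Arm A. The share of all deaths known differed, at 62% and 74%, because more Arm B deaths follow progression. This shows uneven information but does not establish a biased comparison.

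**Conclusion.** The concern holds as a badly fixed contact rule. Two results need only the protocol's PFS and accrual assumptions: a final cut near month 19, and almost no annual contacts by the first interim. The unknown share of post-progression deaths, roughly 60% at month 19 and 42% to 46% at month 24, varied little across the assumptions tried.

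The effect on OS is less certain. With about 65 true deaths, 30 to 57 would be known at month 19 and 39 to 57 at month 24, for power of about 0.50 to 0.80 and 0.63 to 0.80. The width comes from the death share among PFS events (5% to 40%, or to 30% at month 24) and from post-progression survival, neither of which the protocol states. No single power loss should be quoted as the protocol's own. The stated 65 deaths and 85% power are not shown to be wrong. They depend on survival information that the written schedule does not deliver by the cut.

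**What to change.** In Section 6.2.16, with a cross-reference from Sections 9.6.1 and 9.6.2, require a survival-status update timed to each interim and final data cut. It should cover every randomised subject not known to have died and not withdrawn from follow-up, with telephone contact allowed. Record the date last known alive as well as any date of death, so that living and dead subjects are updated alike. This update alone recovers the deaths at issue among subjects who can be reached. More frequent telephone survival contact until the final analysis, for example every 3 months, is an optional addition. The cost is protocol wording and a few phone calls per subject; the OS analysis method is unchanged.
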